[figure not shown]
Randomized trial of
tenofovir disoproxil fumarate dose adjustment VS. switching to tenofovir alafenamide
in tenofovir disoproxil fumarate-experienced chronic hepatitis B patients with renal impairment

SIRB Protocol No. : 657/2562(EC3)

COA no. : SI 798/2019

Document date : 25 Nov 2019

Study protocol

| | Week 0 | Week 12 | Week 24 | Week 36 | Week 48 |
|---|---------------|----------------|----------------|----------------|----------------|
| History taking and physical examination | X | X | X | X | X |
| CBC | X | | | | X |
| Creatinine, BUN, Uric acid, Calcium, Phosphate, Electrolyte | X | X | X | X | X |
| AST/ALT | X | X | X | X | X |
| HBV DNA viral load | | | X | | X |
| urinalysis, urine protein creatinine ratio, urine phosphate | X | X | X | X | X |
| urine β 2-microglobulin | X | X | X | | X |
| urine NGAL | X | X | | | |
| ultrasonography of upper abdomen | | | X | | X |

- Some blood tests may be stored before -20 ° C for later tests.

- Some urine tests may be stored before -30 ° C for later tests.

Monitoring and follow-up guidelines in the event that patients receiving TDF dose adjustment or change to TAF and the kidney function deterioration.

- If the GFR from 40 ml/min or more: Make appointment for examination every 12 weeks

- If the GFR is less than 40 ml/min: Make appointment every month

- If the GFR is less than 30 ml/min: Change to Entecavir (1mg) 1 * 1 po pc

If patient will have to check up earlier than 12 weeks, there will be a travel cost of 300 baht per time.

However, if the patient comes to the same appointment every 12 weeks, there will be no travel cost.

Inclusion criteria

1. Age between 18 - 75 years old

2. Chronic hepatitis B virus infection

3. Reduced renal function and need to adjust the dose of TDF

4. Have an eGFR of ≥ 15 ml / min.

5. HBV DNA viral load levels ≤ 10 U/mL in the last 3 months before participating in the project

6. No HCC by ultrasonography of the upper abdomen or CT 3-phase of liver or MRI liver in the 3 months before participating in the project.

Exclusion criteria

1. HIV infection or hepatitis C or hepatitis D co-infection

2. Decompensated cirrhosis, including variceal bleeding, ascites, hepatic encephalopathy

3. Active hepatocellular carcinoma or during the 3 years after treatment

4. Solid organ transplantation or Bone marrow transplantation

5. Chronic kidney disease caused by glomerulonephritis, tubulo-interstitial nephritis), Obstructive uropathy or autosomal dominant polycystic kidney, and Kidney disease from other causes

6. Diabetes with HbA1c > 8 or uncontrollable hypertension

7. Active malignancy of cancer in other organs in the last 3 years

8. History of receiving non-steroidal anti-inflammatory drugs (NSAIDs) or other nephrotoxic drugs within the past 1 month (except tenofovir)

(For patients receiving NSAIDs after participating in this study, patients were advised to stop taking NSAIDs but not exclude from the study)

9. Receive immunosuppressive drug

10. Pregnancy

Withdrawal or termination criteria

1. GFR reduction was less than 15 ml / min

2. Receive renal replacement therapy

3. Receive a liver or kidney organ transplant.

4. Request to withdraw from their participation in the study.

5. Develop HCC.

Sample size calculation

From a literature review, It was found that the average value of the eGFR level of the TDF group was -5.34 ± 7.69 (n = 45) (95% CI: -7.65 - -3.02) and the mean value of the eGFR in TAF group was $+2.89. \pm 4.26$ (n = 36) (95% CI: 1.45 - 4.33) But from the Siriraj hospital observations during 2018, the mean The eGFR change value level is +5.92 after TDF dose adjustment. Therefore, from the above data, when determining the significance level = 0.05 (type I error = 5%, 2-sided) and power of the test = 80% (type II error = 20%), 33 samples would be needed in each group

$$n = \frac{(Z_{\alpha/2} + Z_{\beta})^2 (\sigma^2)}{(\mu_1 - \mu_2)^2}$$

$n =$ samples would be needed in each group

$\alpha =$ type I error = 0.05 ($Z_{\alpha/2} = 1.96$)

$$\beta = \text{type II error} = 0.20 \quad (Z_{\beta} = 0.84)$$

σ = standard deviation

$\mu_1 - \mu_2$ = The difference of mean values between groups

$$n = \frac{(1.96 + 0.84)^2 (4.26^2)}{(5.92 - 2.89)^2} = 33$$

From the calculations, it was found that at least 33 samples were used per group. After add dropout rate 15%, So 40 samples are to be used per group, a total of 80 people in this study.

Statistical analysis

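### No randomisation method, stratification or baseline eGFR term is described, although GFR bands at 40 and 30 set visit frequency and loss of the assigned drug in both arms

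*Combined protocol and SAP*

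**What the plan says.** On allocation, the only statement is in the title: "Randomized trial of". No sequence generation, blocking, stratification, minimisation or concealment is described. The Sample size calculation fixes the numbers: "So 40 samples are to be used per group, a total of 80 people in this study".

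The Inclusion criteria set the renal range in two items. Item 3 is "Reduced renal function and need to adjust the dose of TDF". Item 4 is "Have an eGFR of ≥ 15 ml / min". No numeric upper limit is given.

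The Monitoring and follow-up guidelines apply to both arms, "in the event that patients receiving TDF dose adjustment or change to TAF and the kidney function deterioration". They hold three rules:
- At 40 or above, visits stay 12-weekly.
- Under 40, visits become more frequent: "If the GFR is less than 40 ml/min: Make appointment every month".
- Under 30, the assigned drug is replaced: "If the GFR is less than 30 ml/min: Change to Entecavir (1mg) 1 * 1 po pc".

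Section 8.8.2 (Inferential statistics) compares changes in eGFR over 48 weeks by repeated measures ANOVA or Friedman's test. It names no baseline eGFR covariate and no stratum factor. The visit table shows creatinine measured at week 0.

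**The concern.** In most trials a baseline value is only prognostic. Here starting eGFR does three things. It is the starting point of the outcome that drives the sample size. It strongly influences who falls below 40 and is seen monthly. It also strongly influences who falls below 30 and stops receiving the assigned drug. If one arm happens to start with more patients near these limits, that arm may have more contact and more patients on the same third drug. The observed eGFR contrast then partly reflects who was allocated where. Neither of the two usual safeguards, stratified allocation and baseline adjustment, is described.

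**Working it through.** **The plan's own figure.** The inputs are a TAF change of +2.89 (SD 4.26), an adjusted-dose TDF change of +5.92, two-sided α of 0.05 and 80% power. The printed formula gives (1.96 + 0.84)² × 4.26² / 3.03² = 15.5. The usual two-group formula doubles this to 31.0, and the t-test version gives 32.02, rounded up to 33. So 33 is right for two groups, although the printed formula omits the factor 2. With 15% dropout, 33 / 0.85 = 38.8, close to the stated 40. Stratifying does not alter these numbers.

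**Chance imbalance.** Let K of the 80 patients start below 40, and let k be the number of them in the first arm of 40. Under unstratified 40:40 allocation, k is hypergeometric (80, K, 40). The difference in shares is |2k − K| / 40, so 20 points means |2k − K| ≥ 8 and 15 points means |2k − K| ≥ 6. K is an assumption, because the documents do not give it.

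| K below 40 | P(≥15 points) | P(≥20 points) |
|---|---|---|
| 8 | 0.057 | 0.005 |
| 16 | 0.161 | 0.048 |
| 23 | 0.137 | 0.047 |
| 24 | 0.222 | 0.087 |
| 31 | 0.168 | 0.066 |
| 32 | 0.254 | 0.110 |
| 39 | 0.179 | 0.073 |
| 40 | 0.263 | 0.117 |

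Even K gives larger tails than neighbouring odd K. An even K allows a count difference of exactly 8 (or 6), whereas an odd K needs 9 (or 7). Both kinds belong in the range.

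**What an imbalance does to the contrast.** Assume 24 against 16 patients of 40 below the limit, half of them changed to entecavir, a mean change of −3 ml/min in those changed, and 0 in the others.
- No drug effect: the arm means are 12 × (−3) / 40 = −0.90 and 8 × (−3) / 40 = −0.60. The crude contrast is off by −0.30.
- On-drug effect of +3 in the first arm: its mean is (12 × (−3) + 28 × 3) / 40 = 1.20, so the crude contrast is 1.20 − (−0.60) = 1.80. With 20 against 20 it would be 1.50 − (−0.75) = 2.25.
- Adjusted for band: the low-band contrast is 0 − (−1.5) = 1.5 and the high-band contrast is 3. Their average is 2.25, the balanced value.

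More generally, suppose patients changed to entecavir differ in mean eGFR change by 2 to 5 ml/min (assumed). A 10-point imbalance in patients changed then moves the contrast by 0.2 to 0.5, and a 20-point imbalance by 0.4 to 1.0. The planned difference is 3.03.

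**What stratifying adds to adjustment.** If half of the patients are below 40 and the arms differ by d in that share, the information in a band-adjusted contrast is 1 − d² of the balanced value. At d = 0.20 this is 0.96, so the standard error rises by √(1/0.96) − 1 = 2.1%. On average, d has SD 0.1125 at K = 40, so d² averages 0.0127. The standard error then rises by √(1/0.9873) − 1 = 0.6%.

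**Limit of a cut at 40.** Assume 40 of the 80 start below 40, and 20 of those below 30. A difference of at least 10 points in the share below 30 has probability 0.44 without stratification. It is still 0.34 with perfect balance at 40.

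**The case against.** The strongest reply is that the band rules are worded identically for both arms. Given starting eGFR, visits and drug changes can differ between arms only through treatment or noise. Adjusting for baseline eGFR therefore also deals with the delivery differences that come from baseline imbalance. This stands, as the 1.80 against 2.25 example shows. A reader might infer that only stratification can correct unequal delivery, and that is not so. The reply does not rescue the plan, because section 8.8.2 names no baseline term.

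Other parts of the case also stand:
- A reader might infer that the trial is not stratified. The documents are silent, and statistics numbered 8.8.1 and 8.8.2 suggest an excerpt from a longer protocol. Silence supports only that no method is described.
- A reader might infer that imbalance biases the comparison. Over repeated randomisations it does not, and the error rate of the test already allows for it.
- The rules act on GFR during follow-up, which treatment can change. Crossings of 40 or 30 can differ between arms even with perfect balance at entry.
- A stratum limit at 40 does not directly balance drug loss at 30.

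Leaving a trial of 80 patients unstratified is an acceptable choice if the plan says so and adjusts for baseline eGFR. The plan does neither.

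**Conclusion.** The point holds as a cheap improvement, not as a flaw that undermines the trial. No allocation method and no baseline eGFR term are described, for the one variable that is the starting point of the outcome and also steers visits and drug changes.

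A 20-point imbalance below 40 has a probability of about 5% to 12% if 23 to 40 of the 80 start there, 0.5% at 8 and 5% at 16. Its effect on the contrast is modest under the assumed inputs, at most about 1.0 ml/min against 3.03. Most of the benefit comes from the baseline term. Stratification adds roughly 1% in precision and protection against an unlucky split. The size rests on an unknown share below 40 and on an assumed effect of changing drug.

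Separately, item 4 of the Inclusion criteria admits patients already under the limit at which the guidelines replace the assigned drug. These passages must be reconciled.

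**What to change.** 1. Describe the randomisation: 1:1, in permuted blocks of varying size, within two strata of week-0 eGFR (<40 and ≥40 ml/min, the plan's own monitoring limit), with the list held by someone who does not enrol patients.
2. In section 8.8.2, include baseline eGFR as a continuous covariate, plus the stratum, in the eGFR comparison. Friedman's test has no place for a covariate, so this needs a linear model.
3. Report by arm the number of unscheduled visits and of patients moved to entecavir. Stratification does not equalise crossings of 40 or 30 after randomisation.
4. Reconcile entry at eGFR ≥15 with the drug change at GFR <30.

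The cost is a second randomisation list and a few sentences. No patients, visits or tests are added, because creatinine is already measured at week 0. The small downside is that this result must be available before allocation. If recruitment has begun, item 1 may no longer be possible; items 2 and 3 can still be adopted, and should be fixed before outcome data are compared by arm.

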8.8.2 Inferential statistics

- Comparison of changes in eGFR, serum phosphate, urine protein creatinine ratio, urine phosphate, urine β 2-microglobulin, AST, ALT, HBV DNA between the treatment with TAF and adjusted dose TDF for 48 weeks by using the Repeated measures ANOVA or Friedman's test.

- Comparison of the change in urine NGAL between the treatment with TAF and adjusted dose TDF for 48 weeks by using Independent T test or Mann whitney test

Data recording and analysis using SPSS programme

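### HBV DNA, at or below 10 U/mL in every patient at entry, is compared only by ANOVA or Friedman's test on changes with no transformation stated; the proportion losing suppression should be the main HBV DNA analysis.

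*Combined protocol and SAP*

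**What the plan says.** Three places in the combined protocol and SAP bear on this.

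- **Inclusion criteria, item 5:** "HBV DNA viral load levels ≤ 10 U/mL in the last 3 months before participating in the project".
- **Study protocol, schedule of assessments:** the row reads "HBV DNA viral load | | | X | | X". The columns are weeks 0, 12, 24, 36 and 48, so HBV DNA is measured at weeks 24 and 48 and not at week 0.
- **8.8.2 Inferential statistics:** one item opens with "Comparison of changes in eGFR, serum phosphate", runs through the other laboratory measures and ends with "HBV DNA between the treatment with TAF and adjusted dose TDF for 48 weeks by using the Repeated measures ANOVA or Friedman's test". HBV DNA is thus handled in the same way as eGFR, phosphate and the transaminases.

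The plan gives no log transformation for HBV DNA, no value to assign to results below the assay limit, no definition of loss of suppression and no non-inferiority margin. It does not plan to report how many patients stayed suppressed. Nor does it say which value serves as the HBV DNA baseline.

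**The concern.** For patients who enter suppressed, the useful question about HBV DNA is how many in each arm lose suppression after the TDF dose adjustment or the switch to TAF. The planned analysis does not answer it, for three reasons.

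1. Everyone starts at or below 10 U/mL, so any material change is upward. Rebounds can differ by orders of magnitude, and on the untransformed scale the largest one sets both the arm mean and its standard error. The test then has little power even when several patients rebound.
2. The alternative offered, Friedman's test, ranks repeated values within patients. It does not compare two independent groups, and ties at the floor would weaken it further.
3. A p-value for a difference in mean change does not say how many patients kept suppression. A non-significant result, which is likely under point 1, could be read as equal viral control.

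**Working it through.** **The plan's own figure.** No sample size or precision is given for HBV DNA. The only calculation is for eGFR change: 33 per group, raised to 40 for 15% dropout. A standard two-sample calculation (difference 5.92 − 2.89 = 3.03, SD 4.26, two-sided 0.05, 80% power) gives 32 per group, close to 33. The formula as printed gives 15.5, which is a separate matter. From this calculation I take only n = 40 per arm enrolled and 40 × 0.85 = 34 evaluable.

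**Step 1. Equal rebounds.** Suppose k of n patients in one arm rebound by the same amount and everyone else shows no change. The two-sample t statistic is then

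t = √[k(n − 1)/(n − k)],

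which does not depend on the size of the rebound. With n = 40:

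- k = 1: t = √(39/39) = 1.00, p ≈ 0.32, whether the rebound is to 10³ or 10⁶ U/mL.
- k = 2: t = √(78/38) = 1.43, p ≈ 0.16 on 78 df.

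For 2 versus 0 of 40, Fisher's exact test gives p = 2 × 780/3160 = 0.49. With equal rebounds, then, the t-test gives the smaller p-value. The weakness of the raw scale appears when rebounds are unequal.

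**Step 2. Unequal rebounds (assumed values).** Let 4 of 33 patients rise from 10 to 100, 1,000, 10,000 and 100,000 U/mL, against 0 of 33 in the other arm, with no change in anyone else.

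- Raw change: mean (90 + 990 + 9,990 + 99,990)/33 = 3,365 U/mL; t = 1.11, p = 0.27. The largest value alone contributes 99,990/33 = 3,030 of that mean.
- log10 change: mean (1 + 2 + 3 + 4)/33 = 0.303, SD 0.918, SE 0.918/√33 = 0.160; t = 1.90, p = 0.06.
- Fisher's test, 4 versus 0 of 33: p = 0.11.

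**Step 3. Rejection rates by simulation.** Assumptions: 34 per arm; suppressed values uniform on 1-10 U/mL; rebounds log-uniform from 10² to 10⁵ U/mL; two-sided 5% level; no losses in the comparator arm. The test on change is a two-sample t-test, which is equivalent to the group-by-time test with two time points.

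| True loss of suppression | Raw mean change | Fisher on proportion | log10 mean change |
|---|---|---|---|
| 10% v 0% | 2% | 12% | 31% |
| 15% v 0% | 8% | 41% | 55% |
| 20% v 0% | 17% | 70% | 77% |

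A separate run at 15% gave about 7%, 40% and 61%. The ordering is the same: raw lowest, log10 highest.

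**Step 4. What a proportion reports.** The exact upper 95% limit for 0 of n is 1 − 0.025^(1/n).

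- n = 40: 8.8%.
- n = 34: 10.3%.

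With 34 per arm, Fisher's test needs 6 versus 0 losses to reach p < 0.05 (p = 0.025); 5 versus 0 gives p = 0.053. The value of the proportion lies in the counts and limits, not in a more powerful test.

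**The case against.** Several points on the other side have force.

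- **Baseline.** A reader might infer from the blank week 0 cell that change in HBV DNA cannot be estimated. The documents do not support that. Criterion 5 requires a result for every patient within 3 months before entry. Ultrasonography follows the same pattern: blank at week 0, with imaging required in the preceding 3 months. The eligibility result could serve as baseline; the gap is that the plan does not say so.
- **Sensitivity.** A reader might infer that the planned methods can show nothing about viral control, or that moving to a proportion costs nothing. Neither follows. With equal rebounds Fisher's test gives the larger p-value (Step 1), and a log10 analysis is more sensitive than Fisher's test throughout Step 3. Only the untransformed mean does badly. The plan does not say which scale it will use, so the raw scale is a reading of its silence.
- **Assay limit.** None is stated. If the assay quantifies below 10 U/mL, values will not all sit at one floor. If its limit is close to 10 U/mL, a single value just above may be noise.
- **Importance.** HBV DNA is one item in a list, and the sample size rests on eGFR. The documents do not name viral control as the main question.

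These points limit the claim and shape the remedy. They do not supply a count of patients who kept suppression, make Friedman's test a between-arm comparison, or turn a null p-value into evidence of maintained control.

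**Conclusion.** The point holds in this form: the planned HBV DNA analysis is poorly matched to a population that enters suppressed, and a non-significant result from it would not show that suppression was kept. On the untransformed scale, power is about 7-8% for a true loss of 15% versus 0%, against about 40% for Fisher's test and 55-61% for log10 change. Those rates depend on the assumed floor values, the assumed spread of rebounds and 34 evaluable per arm. The problem of interpretation does not depend on them. The point should be acted on, but it does not affect the eGFR comparison or the sample size.

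**What to change.** Amend 8.8.2 as follows.

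1. Make the main HBV DNA analysis the number and proportion in each arm with HBV DNA above 10 U/mL, the trial's own entry threshold, at week 24 or week 48. Give exact 95% limits per arm and the between-arm difference with its 95% CI.
2. Replace the raw-scale ANOVA/Friedman analysis of HBV DNA with a supportive between-arm comparison of log10 HBV DNA. Fix in advance the value assigned to below-limit results, and name the eligibility result as baseline.
3. List every individual value above 10 U/mL, so that results just over the threshold can be told apart from clear rebounds.
4. State in advance how missing samples, and samples taken after a change to entecavir, are counted.

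**Cost.** Wording only: no extra patients, visits or samples. Dichotomising is less sensitive than the log10 analysis, which is why the latter is kept as support. With about 34 evaluable per arm, even zero losses leaves an upper limit of about 10%, and the report should say so.

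### Withdrawal criterion 1 names a GFR fall of under 15 ml/min where a GFR level below 15 is meant, and nothing says creatinine is recorded after it is met

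*Combined protocol and SAP*

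**What the plan says.** Under the heading Withdrawal or termination criteria, the first of five items is "GFR reduction was less than 15 ml / min". The second and third are "Receive renal replacement therapy" and "Receive a liver or kidney organ transplant"; the other two are a patient's request to withdraw and development of HCC.

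The other GFR thresholds in the protocol are levels. Inclusion criterion 4 is "Have an eGFR of ≥ 15 ml / min". The monitoring guideline, which applies "in the event that patients receiving TDF dose adjustment or change to TAF and the kidney function deterioration", states "If the GFR is less than 40 ml/min: Make appointment every month" and "If the GFR is less than 30 ml/min: Change to Entecavir".

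Creatinine is scheduled at weeks 0, 12, 24, 36 and 48. The visit table does not mention patients who have met a withdrawal criterion. The one explicit statement about staying in the study concerns NSAID use after entry: "patients were advised to stop taking NSAIDs but not exclude from the study" (Exclusion criteria, item 8).

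Section 8.8.2 compares eGFR change between arms over 48 weeks by repeated measures ANOVA or Friedman's test. It gives no rule for missing visits or for data after withdrawal.

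**The concern.** There are two linked faults.

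1. **The printed condition is the wrong one.** A reduction of less than 15 is a small fall. Taken at its word, the rule removes patients whose renal function is nearly stable and retains those who lose 15 ml/min or more.
2. **The intended condition acts on a compared outcome.** If a level below 15 is meant, this is the only withdrawal criterion triggered by a value of eGFR itself. If withdrawal ends data collection, the lowest eGFR values leave the comparison of randomised arms. Repeated measures ANOVA and Friedman's test, in standard form, need every visit, so such a patient's earlier eGFR values would be lost as well.

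At stake is who leaves a randomised trial, and whether the renal comparison includes the patients with the worst renal course.

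**Working it through.** **Which reading is intended.** Four things point to a level below 15:

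- the entry floor uses the same number as a level;
- the rules at 40 and 30 are levels;
- the next criterion, renal replacement therapy, belongs with very low GFR;
- the literal rule cannot be operated, as shown below.

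**Inputs** (Sample size calculation): TAF change +2.89, SD 4.26; dose-adjusted TDF change +5.92, with no SD given; 40 patients per arm. The planned difference is 5.92 − 2.89 = 3.03.

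**Assumptions:** the week-48 change is normal; there is one assessment; the TDF SD lies between 4.26 (used in the sample size) and 7.69 (the literature TDF group).

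**Literal reading.** If a stable or rising GFR counts as a reduction of under 15, the share meeting the rule is P(change > −15) = 1 − Φ((−15 − mean)/SD).

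- TAF: 1 − Φ(−17.89/4.26) = 1 − Φ(−4.20) = 99.999%.
- TDF, SD 4.26: 1 − Φ(−20.92/4.26) = 1 − Φ(−4.91), above 99.99%.
- TDF, SD 7.69: 1 − Φ(−20.92/7.69) = 1 − Φ(−2.72) = 99.67%.

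At most 40 × 0.00326 = 0.13 patients per arm would remain.

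If only true falls count, the share is P(−15 < change < 0) = Φ(−mean/SD) − Φ((−15 − mean)/SD).

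- TAF: Φ(−0.68) − Φ(−4.20) = 24.9%.
- TDF: 8.2% (SD 4.26) to 21.7% (SD 7.69).

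These figures show that the wording is wrong. They do not forecast what investigators would do.

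**Intended reading.** A patient with baseline eGFR B meets the rule if the change is below c = 15 − B, with probability Φ((c − mean)/SD). The mean change among those who remain is mean + SD·φ(a)/(1 − Φ(a)), where a = (c − mean)/SD. The plan gives no baseline distribution, so a range is shown. In the two TDF-dependent columns, the first value uses SD 4.26 and the second SD 7.69.

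| Baseline eGFR | TAF meeting rule | TDF meeting rule | TDF − TAF among those remaining (planned 3.03) |
|---|---|---|---|
| 30 | 0.001% | <0.001% to 0.33% | 3.03 to 3.11 |
| 35 | <0.001% | <0.001% to 0.04% | 3.03 to 3.04 |
| 40 | <0.001% | <0.001% to 0.003% | 3.03 to 3.03 |
| 25 (illustrative) | 0.12% | 0.01% to 1.9% | 3.01 to 3.38 |
| 20 (illustrative) | 3.2% | 0.5% to 7.8% | 2.78 to 3.93 |

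Worked case, baseline 30, TDF SD 7.69: c = −15 and a = −20.92/7.69 = −2.72, so 0.33% meet the rule, or 0.13 of 40. The mean change among those remaining rises from 5.92 to 6.00. The TAF mean stays at 2.89, and the unrounded difference is 3.11.

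The rows at 25 and 20 are only illustrative. Below 30 the plan moves patients to entecavir, so the TAF and TDF inputs no longer describe them. That rule is headed for deterioration, so its use for patients who enter below 30 is also unclear.

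**Sensitivity.** The literature TDF mean (−5.34 ± 7.69), which the sample size did not use, gives Φ((−15 + 5.34)/7.69) = Φ(−1.26) = 10.5% at baseline 30, 2.8% at 35 and 0.5% at 40.

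**The case against.** The strongest reply has three parts.

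- **The wording is a translation slip.** The English is irregular throughout, a site would read it as reduced to below 15, and nobody could apply the literal rule. That is probably right about behaviour, and it is why the point is rated minor. But this is an operating threshold for leaving the trial, and it should state the correct condition. Reading past it also does not settle whether creatinine is still collected.
- **The plan already keeps declining patients under observation off study drug.** The entecavir switch below 30 is not among the withdrawal criteria, and visits become monthly below 40. This is fair, and it confines the gap to patients below 15. It does not close the gap, because 15 is where the plan moves from changing drug to withdrawal or termination.
- **The loss of data is an inference from silence, and the numbers are tiny.** Both points stand as qualifications. The plan does not say whether withdrawal ends treatment, visits or data collection, nor how incomplete cases are analysed. The 0.13 of 40 is not a strict bound: it depends on normality, an SD no larger than 7.69 and a single assessment. Crossing 15 at any of several visits would be somewhat more frequent and was not computed. The 10.5% deserves little weight, since the plan sets the literature TDF result against its own dose-adjustment figure.

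**Conclusion.** The concern holds, at minor severity. Criterion 1 is wrong as written. That a level below 15 is intended is an inference, but the rest of the protocol supports it well. The follow-up gap is also real: no section says creatinine continues once the criterion is met.

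The numerical consequence is small: close to nil at a baseline of 30 or more on the sample-size values, under the assumptions set out above. Below 30 the direction of any bias is uncertain. The lower TAF mean shrinks the difference if the SDs are equal, and a wider TDF SD enlarges it. The sample size is not affected.

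**What to change.** Reword criterion 1 to: *eGFR falls to below 15 ml/min*. Then add two statements.

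- **Follow-up:** meeting the criterion means stopping any remaining study drug (a patient below 30 should already be on entecavir), not leaving follow-up. Scheduled creatinine is recorded to week 48, or until renal replacement therapy, transplant or withdrawal of consent.
- **Analysis (section 8.8.2):** the patient is analysed in the randomised arm with all available visits, for example by a linear mixed model in place of repeated measures ANOVA. The mixed model goes beyond the wording correction, but without a method that accepts incomplete visits the retained data may not be used.

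The cost is a short amendment and, for the few patients concerned, at most the four creatinine visits already scheduled at weeks 12, 24, 36 and 48.

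### Renal replacement therapy, transplant and new HCC are handled as leaving the trial, so patients with renal failure drop out of the 48-week eGFR comparison by default and an arm with more of them would look better than it truly is

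*Combined protocol and SAP*

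**What the plan says.** The list headed "Withdrawal or termination criteria" has five items. Item 2 is "Receive renal replacement therapy", item 3 is "Receive a liver or kidney organ transplant", and item 5 is the development of HCC. Item 4, on the same footing, is "Request to withdraw from their participation in the study". Item 1 reads "GFR reduction was less than 15 ml / min". Its wording is unclear, but it may mean a GFR below 15 ml/min.

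Section 8.8.2 plans a "Comparison of changes in eGFR, serum phosphate, urine protein creatinine ratio, urine phosphate" and other markers "between the treatment with TAF and adjusted dose TDF for 48 weeks by using the Repeated measures ANOVA or Friedman's test", run in SPSS. The visit table schedules creatinine at weeks 0, 12, 24, 36 and 48, and upper abdominal ultrasound at weeks 24 and 48.

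The documents define no analysis set, give no rule for missing values, provide no follow-up after withdrawal, and plan no comparison or count of renal replacement therapy, transplant or HCC by arm. The only allowance for lost patients is the 15% added to the sample size.

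**The concern.** The trial compares renal change in patients whose kidneys are already impaired. Renal replacement therapy and kidney transplant are the extreme end of that outcome, yet reaching them counts as leaving the study. Nothing is then collected to week 48, and a complete-series analysis also discards the falling eGFR values already recorded at the earlier visits.

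The comparison then describes patients who did not fail. If renal failure is commoner in one arm, that arm loses its worst values and its mean change is too favourable. Since 8.8.2 plans no count of these events by arm, a reader of the results would have no planned figure that reveals the imbalance.

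HCC raises a different problem. It does not prevent creatinine from being measured, so a patient found to have HCC at the week-24 ultrasound loses the week-36 and week-48 values without need, and a liver outcome goes unreported.

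**Working it through.** **The plan's own figure.** The planned difference is 5.92 - 2.89 = 3.03 ml/min, with SD 4.26, two-sided alpha 0.05 and power 80%. A two-sample t-test calculation gives 32.02, so 33 per group, as stated. (The formula as printed lacks a factor of 2 and gives 15.5; that is a separate matter.) Allowing for 15% dropout, 33/0.85 = 38.8, so 39; the plan uses 40. Losing 15% of 40 leaves 34 per arm and power of about 83%. The allowance therefore protects power. It does nothing about which patients are lost.

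**Bias from removing renal failures.** Inputs:
- 40 patients per arm (sample size section).
- Mean change m = +2.89 among retained patients in both arms (the plan's TAF figure; its use for both arms is an assumption).
- k patients removed from one arm only, each with an eGFR change d. The documents give neither k nor d, so both are assumed.

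Mean of all randomised patients in the affected arm = [(40 - k) × m + k × d]/40.
Mean of those analysed = m.
Bias = the second minus the first = k × (m - d)/40.

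| k | d (ml/min) | Bias (ml/min) | Share of 3.03 |
|---|---|---|---|
| 0 | any | 0 | 0% |
| 1 | -10 | 12.89/40 = 0.32 | 11% |
| 1 | -15 | 17.89/40 = 0.45 | 15% |
| 2 | -10 | 25.78/40 = 0.64 | 21% |
| 2 | -15 | 35.78/40 = 0.89 | 30% |
| 3 | -10 | 38.67/40 = 0.97 | 32% |
| 3 | -15 | 53.67/40 = 1.34 | 44% |

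If both arms lose the same number of patients with similar changes, the two biases cancel and the bias in the difference is about zero.

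**Which falls are possible.** Entry is allowed from eGFR 15 ml/min. A patient entering at 15 cannot lose more than 15, and losing 15 would take eGFR to zero. Larger falls apply only to patients who enter well above the floor.

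**Could the order of the arms reverse?** Suppose the retained patients in the affected arm average +5.92 and the other arm averages +2.89. The true means are equal when k × (5.92 - d)/40 = 3.03, so k = 121.2/(5.92 - d). For d = -15 this is 121.2/20.92 = 5.8. For d = -20 it is 121.2/25.92 = 4.7. For d = -30 it is 121.2/35.92 = 3.4. Reversal therefore needs about 4 to 6 one-sided events of 40, more than the 1 to 3 illustrated.

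**The case against.** The strongest reply is that these events may be rare. There are 80 patients and 48 weeks, and decompensated cirrhosis, prior transplant, recent HCC and kidney disease from other causes are excluded. The plan expects eGFR to rise in both arms, and nothing in it shows that events would differ by arm. This stands as a limit on size, and it is why zero belongs in the range.

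Item 1, if it means GFR below 15, would usually remove a declining patient before dialysis or kidney transplant, so it is probably the main renal route out. This also stands. It widens the point, because item 1 would be the same problem.

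The loss of earlier eGFR values comes from a complete-series method without a missing-data rule, and so affects every dropout. That is true. What is particular here is that the plan's own rule selects patients by their outcome.

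A reader might also infer more than the documents support:
- That the plan orders data to be discarded. It does not say so. The loss follows from the withdrawal rule, the named methods and the absence of any other provision.
- That the harmful arm would overtake the other. None of the illustrated cases reaches 3.03. The supported claim is that an arm looks better than it truly is.
- That entrants near eGFR 15 could lose 20 to 25 ml/min, which would give biases such as 2 × 22.89/40 = 1.14 or 3 × 27.89/40 = 2.09. Such falls are impossible from that starting level.
- That HCC removes the worst renal values. Nothing in the documents links HCC to falling eGFR, and HCC found at the week-48 ultrasound costs no scheduled eGFR value.

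**Conclusion.** The point holds and should be corrected before analysis. Followed as written, the plan drops patients from its renal comparison because of their renal outcome, and it does not count them.

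The size cannot be fixed from the documents. It is zero without events and about zero if they are balanced. On the stated assumptions (40 per arm, retained mean +2.89, 1 to 3 events in one arm only, changes of -10 to -15 ml/min) it is about 0.3 to 1.3 ml/min, or 11% to 44% of the planned difference. For HCC the loss is one of data and of a reported outcome, with no clear direction of bias in eGFR.

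**What to change.** Separate stopping study treatment from ending follow-up:

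1. State that only withdrawal of consent ends data collection. Patients with renal replacement therapy, transplant or HCC, or who meet item 1 once its meaning is clarified, stay in their randomised arm with the scheduled bloods to week 48.
2. Report the numbers with renal replacement therapy, transplant and HCC by arm, beside the eGFR result.
3. Analyse eGFR with a method that keeps incomplete series, for example a linear mixed model, which SPSS offers. Use all values recorded before renal replacement therapy or kidney transplant, since later ones do not reflect the patient's own kidney function.
4. Add a sensitivity analysis that ranks renal-failure patients worst, because a mixed model relies on the missing values being predictable from the observed ones. Define renal failure for this purpose in advance.

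The protocol already works this way elsewhere: patients who take NSAIDs after entry stay in the study, and the change of drug in the monitoring guidance is not a withdrawal criterion.

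The cost is a paragraph in the protocol, a changed analysis method in 8.8.2 with the definitions it needs, and a few retained visits that are already scheduled. eGFR after HCC treatment may be noisier. Clinical management of these patients stays with the investigators.
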